### 4.2 Secondary Endpoints

#### 4.2.1 Preliminary Antitumor Activity

Tumor assessments will be performed every 8 weeks ( $\pm$  1 week) during the treatment period (Cycle 1 Day 1 through Cycle 6 Day 56), and at planned timepoints during the clinical follow-up period. In addition, subjects who discontinue study drug for reasons other than progression will continue to have tumor assessments completed every 12 weeks for the first year and then continue to receive scans per standard of care guidelines for follow-up or at a minimum of every 6 months until disease progression or withdrawal of consent.

Changes in tumor measurements and tumor response will be assessed by the investigator using the Response Evaluation Criteria in Solid Tumors (RECIST) version 1.1 for subjects with solid tumors and using the revised International Working Group (IWG) Criteria for subjects with B-cell NHL and Follicular Lymphoma. Investigators will also report the number and size of new lesions that appear while on-study. Endpoints will be defined based on all available tumor assessments.

The following set of efficacy study-level endpoints will be used.

- **Objective Response Rate (ORR):** The total number of subjects whose best overall response (BOR) is either a complete response or partial response for solid tumors and complete remission or partial remission for B-cell NHL, divided by the total number of subjects in the population of interest. Hereafter, complete response for solid tumors and complete remission

for B-cell NHL will both be referred to as complete response (CR); partial response for solid tumors and partial remission for B-cell NHL will both be referred to as partial response (PR).

- Best Overall Response: The subject's best response designation over the study as a whole, recorded between the date of first study drug administration and the date of objectively documented progression or relapse per RECIST 1.1 or IWG, with subsequent confirmation, or date of subsequent anti-cancer therapy, whichever occurs first in the study.
  - ◆ A minority of subjects may continue treatment beyond confirmed progression or relapse, as described in Protocol Section 3.5.1. For these subjects, the BOR should be determined based on response designations recorded up to the time of the initial RECIST 1.1 defined progression or IWG defined relapse or progressive disease.
  - ◆ Complete or partial responses in solid tumors may be claimed only if changes in tumor measurements are confirmed by a consecutive assessment meeting the criteria for response or remission and performed no less than 4 weeks (28 days) after the criteria for response were first met.
  - ◆ When stable disease (SD) is believed to be the best response, it must meet the protocol specified minimum time from baseline. Measurements must have met the SD criteria at least once after study entry. The minimum criteria for SD duration (8 weeks) must have been satisfied (considering the  $\pm 1$  week tumor assessment window, 49 days will be used to derive SD).
- **Median Duration of Overall Response (mDOR):** The significance of ORR is assessed by its magnitude and duration of response. DOR is computed only for subjects with objectively defined CR or PR, and is defined as the time from first response to the subsequent date of objectively documented disease progression based on the criteria (RECIST 1.1) or relapse based on IWG, or death due to any cause, if death occurred within 100 days after last dose, whichever occurs first. If death is more than 100 days after last dose, then duration of response is censored at the last tumor assessment date. Subjects who remain alive and have not progressed nor received subsequent therapy, will have their DOR censored on the date of their last tumor assessment. Subjects who receive subsequent therapy will be censored at the start of subsequent therapy.
- **Progression Free Survival Rate (PFSR) at Week X:** The proportion of subjects remaining progression free and surviving at X weeks, where X is a specific length of time, eg, 24 weeks, which will be determined by the data for each interim or final analysis and will be documented in the data presentation plan (DPP). The proportion will be calculated by the product-limit method (Kaplan-Meier estimate) which takes into account censored data.
  - Progression Free Survival (PFS): The PFS for a subject is defined as the time from the date of first dose of study drug to the date of the first documented disease progression or relapse, or death due to any cause, if death occurred within 100 days after last dose. Clinical deterioration in the absence of radiographic evidence is not considered progression for the purpose of determining PFS. Subjects who die within 100 days after last dose without a reported prior progression will be considered to have progressed on the date of their death. Subjects who remain alive and have not progressed will be censored on the date of the last tumor assessment. Subjects who did not have any on

study tumor assessment and did not die within 100 days after last dose of study medication will be censored on the date of first dose of study medication.

#### **4.2.2 Pharmacokinetic Endpoints**

The following PK parameters of urelumab derived from serum concentration time profile of subjects using non-compartmental analysis may be included for urelumab PK analysis, depending on the availability of data.

- Cmax ( $\mu\text{g}/\text{mL}$ ) (maximum concentration)
- Tmax (hr) (time to maximum concentration)
- AUC(0-T) ( $\mu\text{g} \cdot \text{hr}/\text{mL}$ ) (area under the plasma concentration-time curve, 0 to time of last quantifiable concentration)
- AUC(TAU) ( $\mu\text{g} \cdot \text{hr}/\text{mL}$ ) (area under the concentration-time curve in one dosing interval, 0 to 28 days)
- Ctrough (trough concentration)
- Ceoinf (end of infusion concentration)

In addition, the following PK parameters of nivolumab will be calculated at specified visits.

- Ceoinf (end of infusion concentration)
- Ctrough (trough concentration)
- AUC(0-T) ( $\mu\text{g} \cdot \text{hr}/\text{mL}$ )
- AUC(TAU) ( $\mu\text{g} \cdot \text{hr}/\text{mL}$ ) (area under the concentration-time curve in one dosing interval, 0 to 14 days)
- Cmax ( $\mu\text{g}/\text{mL}$ )
- Tmax (hr)

#### **4.2.3 Immunogenicity**

Immunogenicity of urelumab and nivolumab are measured by the detection of human antibodies against urelumab and nivolumab, respectively. Endpoints for the study are incidence rates of persistent positive Human Anti-Drug Antibody (ADA) as well as neutralizing positive ADA from initiation of each drug treatment up to and including the follow-up period of the last study drug dosed.

Based on recommendation from BMS Immunogenicity Council and White Paper on Assessment and Reporting of the Clinical Immunogenicity of Therapeutic Proteins and Peptides - Harmonized Terminology and Tactical Recommendations by Shankar et al, and the Food and Drug Administration (FDA) Guidance for Industry Immunogenicity Assessment for Therapeutic Protein Products, the following definitions will be applied for urelumab and nivolumab separately:

##### **4.2.3.1 ADA Status of a Sample**

- **Baseline ADA-Positive Sample:** ADA is detected in the last sample before initiation of treatment

- **Baseline ADA-Negative Sample:** ADA is not detected in the last sample before initiation of treatment
- **ADA-Positive Sample:** After initiation of treatment, (1) an ADA detected (positive seroconversion) sample in a subject for whom ADA is not detected at baseline, or (2) an ADA detected sample with ADA titer to be at least 4-fold or greater ( $\geq$ ) than baseline positive titer
- **ADA-Negative Sample:** After initiation of treatment, ADA not positive sample relative to baseline

#### 4.2.3.2 ADA Status of a Subject

- **Baseline ADA-Positive Subject:** A subject with baseline ADA-positive sample
- **ADA-Positive Subject:** A subject with at least one ADA-positive sample at any time after initiation of treatment
  - *Persistent Positive (PP):* ADA-positive sample at 2 or more consecutive timepoints where the first and last ADA-positive samples are at least 16 weeks apart
  - *Not PP - Last Sample Positive:* Not persistent positive with ADA-positive sample in the last sampling timepoint
  - *Other Positive:* Not persistent positive but some ADA-positive samples with the last sampling being negative
  - *Neutralizing Positive:* At least one ADA-positive sample with neutralizing antibodies detected
- **ADA-Negative Subject:** A subject with no ADA-positive sample after the initiation of treatment

The image consists of a series of horizontal bars of varying lengths and positions. The bars are mostly black on a white background, with some white bars appearing in the gaps. The image is heavily processed, appearing as a binary black and white pattern. The bars are arranged in a staggered, non-overlapping manner, creating a sense of depth or a stepped structure. The lengths of the bars vary significantly, with some being very short and others being quite long. The overall effect is abstract and geometric.

## **5 SAMPLE SIZE AND POWER**

### **5.1 Dose Escalation**

In dose escalation, the sample size at each dose cannot be determined exactly, as it depends on the number of observed toxicities. Between 3 and 12 subjects approximately are expected to be treated during dose escalation in each dose level.

### **5.2 Cohort Expansion**

#### **5.2.1 Stage 1**

During Stage 1 of cohort expansion, approximately 20 subjects in each tumor type will be treated at the MTD/HAD dose level and schedule. A sample size of approximately 20 subjects in each tumor type in Stage 1 is intended to provide a better picture of the safety of each regimen. For example, if a low grade adverse event were observed in 3 or fewer patients, the 90% 1-sided upper confidence interval would be 30%. In addition, it allows for a futility assessment. In general, if the true response rate is 20%, 30%, 40%, or 50%, the probability of seeing 4 or more responses in the 20 patients is 58.9%, 89.3%, 98.4%, and 99.9%, respectively. If the true response rate is 30%, the likelihood of seeing less than 4/20 responses is 10.7% (false negative rate). Conversely, if the true response rate is 10%, the likelihood of seeing 4 or more responses is 13.3% (False Positive Rate).

#### **5.2.2 Stage 2**

[figure not shown]
During Stage 2 of cohort expansion, up to approximately 20 additional subjects will be treated in each tumor type. This will allow for further establishment of the safety profile of the combination and a preliminary assessment of efficacy. The total of approximately 40 subjects (20 from Stage 1 Expansion and 20 from Stage 2) is designed to provide higher precision around estimates of safety and preliminary efficacy. If in a cohort of 40 subjects 7, 10, or 15 responses are observed, then the lower limit of the one-sided 90% exact binomial CI for the ORR is 10%, 16%, and 27% respectively. These calculations are made using the Clopper-Pearson method for exact confidence intervals. If the true ORR in a tumor type is 50%, then with 40 subjects in a tumor type, there is 96% chance of observing at least 15 responses, and 87% chance of observing at least 17 responses, and there is 8% chance of observing 15 or fewer responses (false negative rate).

## **6 STUDY PERIODS, TREATMENT REGIMENS AND POPULATIONS FOR ANALYSES**

### **6.1 Study Periods**

Subjects will complete up to four periods of the study (Screening, Treatment, Clinical/Safety Follow-up, and Survival/Long-term Follow-up). The total time on study for any individual subject is expected to be approximately 3.1 years. A study schematic is presented in [Figure 1](#).

**Figure 1:** Study Schematic

CR = complete response; PR = partial response; SD = stable disease; PD = progressive disease

### 6.1.1 Screening Period

The screening period will last for 28 days. Screening period begins by establishing the subject's initial eligibility and signing of the informed consent form (ICF). Subject is enrolled using the Interactive Voice Response System (IVRS).

Baseline evaluations or events will be defined as evaluations or events that occur before the date and time of the first dose of either study drug. In cases where the time (onset time of event or evaluation time and dosing time) is missing or not collected, the following definitions will apply:

- Pre-treatment AEs will be defined as AEs with an onset date prior to, but not including, the date of the first dose of either study drug.
- Baseline evaluations (laboratory tests, pulse oximetry, and vital signs) will be defined as evaluations with a date on or prior to the date of first dose of either study drug, unless otherwise specified, since these procedures are to be performed prior to dosing as specified in Protocol Section 5.3 and Table 5.1-2.

If there are multiple valid assessments at baseline, then the assessment that is closest to the date (and time, if collected) of the first dose of study treatment will be used as the baseline in the analyses. If multiple assessments are collected at the same date (and time, if collected), then the assessment with the latest database entry date (and time, if collected) will be considered as baseline.

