Vital Signs	X	X	X	X		
Vital signs (body temperature, seated blood pressure, heart rate and respiratory rate) will be obtained before the BMS-936558 infusion, after the BMS-936558 infusion, before the BMS-663513, and after the BMS-663513 infusion.
 
Subjects must be observed for 30 minutes after the BMS-663513 infusion before discharge. If any vital sign is abnormal at the final check, the subject must be observed further for a period of time, as clinically indicated.
 
The start and stop time of the study drug infusion should be documented. If there are any new or worsening clinically significant changes since the last examination, report changes on the appropriate non-serious or serious adverse event page.
 
See Section 4.5.9 for treatment of infusion reaction.

Non-Serious Adverse Events	X	X	X	X		Non-serious AEs will be collected starting with the first dose of study medication and through 100 days after discontinuation of dosing.
Serious Adverse Events	X	X	X	X		All SAEs must be collected starting at the time a subject signs informed consent and through 100 days after discontinuation of dosing. SAEs should be approved in TAO within 5 business days of entry
	■	■	■	■		■
Electrocardiogram (ECGs)	X					12-lead ECG (if performed on same day as study drug administration it is to be performed prior to dosing).

Table 5.1-2: On Treatment Procedural Outline (CA186107) - Initial Treatment

Procedure	Cycles 1-6					Notes
	D 1a (-2 days)	D 15 (± 2 days)	D 29 (± 2 days)	D 43 (± 2 days)	D 49-56	
Chest Radiograph						As clinically indicated.
Oxygen Saturation Levels	X	X	X	X		Collect pulse oximetry at rest prior to dosing.
Laboratory Tests	X	X	X	X		On study labs (including pregnancy testing) to be done on site/local. Within 72 hrs prior to dosing
Chemistry (excluding LFTs)	X	X	X	X		Includes assessments for sodium, potassium, chloride, total serum calcium, magnesium, carbon dioxide, phosphorus, BUN, creatinine, glucose, total protein, albumin, amylase, lipase, CRP, ferritin, LDH.
CBC with differential & platelets	X	X	X	X		Should also be collected at each timepoint where samples for immunophenotyping are collected as listed in Table 5.7-1

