Body weight and performance status should be assessed at each on-study visit. Vital signs will be obtained before the nivolumab infusion, after the nivolumab infusion, before the urelumab infusion, and after the urelumab infusion. Subjects must be observed for 30 minutes after the urelumab infusion before discharge. If any vital sign is abnormal at the final check, the subject must be observed further for a period of time, as clinically indicated. The start and stop time of the study drug infusion should be documented. Any new or worsening clinically significant changes must be reported on the appropriate non-serious or serious adverse event page.

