### **7.6.9 *Vital Signs and Physical Findings***

#### **Summary:**

The following parameters and their corresponding change from baseline will be summarized by timepoint and treatment group.

- Vital Signs

- Body weight and performance status

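### The SAP's missing-time rule for baseline assumes Day 1 vital signs all precede dosing, but three of the four scheduled readings follow the first infusion, and the tie-break can pick one of them

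*SAP*

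**What the plan says.** SAP 6.1.1 starts from a sound general rule: a baseline evaluation is one made before the date and time of the first dose of either drug. It then gives a fallback, which applies "In cases where the time (onset time of event or evaluation time and dosing time) is missing or not collected". Under it, baseline laboratory tests, pulse oximetry and vital signs are "evaluations with a date on or prior to the date of first dose of either study drug", unless specified otherwise. The reason given is "since these procedures are to be performed prior to dosing as specified in Protocol Section 5.3 and Table 5.1-2".

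Two tie-breaks follow. With several valid assessments, the SAP uses "the assessment that is closest to the date (and time, if collected) of the first dose of study treatment". If these share the same date (and time, if collected), "then the assessment with the latest database entry date (and time, if collected) will be considered as baseline".

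For vital signs, the two protocol places cited say this:

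- Table 5.1-2, Vital Signs row, with Day 1 marked: "will be obtained before the BMS-936558 infusion, after the BMS-936558 infusion, before the BMS-663513, and after the BMS-663513 infusion".
- Section 5.3: "Vital signs will be obtained before the nivolumab infusion, after the nivolumab infusion, before the urelumab infusion, and after the urelumab infusion".

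The vital-sign baseline is used in SAP 7.6.9: "The following parameters and their corresponding change from baseline will be summarized by timepoint and treatment group".

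**The concern.** The fallback can use the date alone only if every reading taken on the first-dose day precedes dosing. The SAP says so and cites two protocol places in support, but for vital signs those places show otherwise. Neither tie-break favours the pre-dose reading, and the second may favour the last one taken.

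If a post-infusion reading becomes baseline, any shift in temperature, blood pressure or heart rate during the first infusion is built into the reference value. That subject's changes from baseline are then measured from a treated value. Protocol 4.5.9 lists fever and blood pressure changes among the possible signs of an infusion reaction, so these are parameters for which the reference value matters.

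**Working it through.** The plan gives no figure to reproduce, so the check applies the rules of SAP 6.1.1, in order, to the protocol's Day 1 schedule, assuming no evaluation times.

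**Is the stated reason true for each item?**

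| Item | Timing in Table 5.1-2 | Reason holds? |
|---|---|---|
| Laboratory tests | within 72 hours before dosing | yes |
| Pulse oximetry | at rest, before dosing | yes |
| Vital signs | before and after each infusion | no |

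**Which Day 1 readings follow study drug?** Protocol 3.1.2 gives nivolumab first and urelumab at least 30 minutes after that infusion ends. The pre-urelumab reading is therefore also a post-nivolumab reading.

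| Vital-sign reading | Follows study drug? | Meets date-only rule? | Days before first-dose date |
|---|---|---|---|
| Screening, earlier date | no | yes | 1 or more |
| Day 1, before nivolumab | no | yes | 0 |
| Day 1, after nivolumab | yes | yes | 0 |
| Day 1, before urelumab | yes | yes | 0 |
| Day 1, after urelumab | yes | yes | 0 |

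So 3 of 4 Day 1 readings (3/4 = 75%) follow the first infusion.

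**Applying the tie-breaks without times.**

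1. Closest date: the four Day 1 readings tie at 0 days and displace any reading from an earlier date.
2. Latest database entry: if entry follows collection order, which is an assumption, the post-urelumab reading is selected. In another order, it could be any of the four. If all four carry the same entry stamp, the SAP gives no further rule.

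**Effect on a change from baseline.** Let Y0 be the pre-nivolumab reading, Yb the reading selected as baseline and Yt a later one. Then

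Yt − Yb = (Yt − Y0) − (Yb − Y0).

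The subject's change is off by −(Yb − Y0) at every later timepoint, and is 0 at the selected reading itself. In a mean over n subjects of whom m are affected, with average first-day shift d among those m, the mean moves by −(m/n) × d. The documents give neither m nor d. Over the whole range, the displacement runs from 0 (m = 0) to −d (m = n).

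**The case against.** The governing rule is correct and uses date and time. The criticised text is only a fallback, and nothing in the documents shows that vital-sign times go uncollected. Infusion start and stop times are to be documented. If the trigger means that evaluation time and dosing time must both be missing, a recorded dosing time would keep the fallback from applying. The qualifiers about valid assessments and other specifications leave some room to exclude a reading labelled post-infusion. Only one of the three items in the sentence is wrong, and both cited places do include a pre-nivolumab reading.

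Most of this stands, and it limits the size of the point. It does not rescue the rule. The SAP itself provides for uncollected times, and the protocol does not explicitly require a clock time for each vital-sign reading. On the strict reading of the trigger, a vital sign with no time but a known dosing time has no usable rule, because the main rule also needs the evaluation time. No exception for vital signs is written in the SAP text available.

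A reader might infer that post-infusion fever, low blood pressure or fast heart rate would be lost from the safety evaluation. The documents do not support that. Clinically significant new or worsening changes go on the adverse event pages, and the adverse event tables do not use this baseline. Infusion reactions are a separate category of events of special interest. SAP 7.6.9 summarises the observed values as well as the changes, and vital signs are listed.

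**Conclusion.** Wrong as written, of minor severity. The fallback rests on a premise that both of its own references contradict for vital signs, and its tie-break can then make a post-infusion reading the baseline. The consequence is bias in the vital-sign change-from-baseline summaries of SAP 7.6.9, only for subjects without usable times. Their number is not stated and may be zero.

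Three stronger readings are tempting but go too far:

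- That every vital-sign change summary is measured from a treated value. Where evaluation and dosing times exist, the main rule excludes post-infusion readings.
- That every affected subject gets the post-urelumab reading, making the Day 1 post-urelumab change zero. This needs missing times and also separate entry in collection order with distinguishable stamps. The documents describe neither how often times are missing nor how vital signs are entered.
- That the primary endpoint is compromised. Protocol 8.3.1 names adverse events and laboratory abnormalities as the primary endpoints. SAP 4.1 adds vital-sign abnormalities to what is examined, but neither makes the vital-sign change from baseline a primary measure.

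**What to change.** In SAP 6.1.1:

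1. Correct the rationale so that it covers laboratory tests and pulse oximetry only, and remove vital signs from the date-only rule.
2. Where times are missing, define the vital-sign baseline as the Cycle 1 Day 1 reading labelled as taken before the nivolumab infusion. If that reading is absent or unlabelled, use the last reading dated before Day 1. Do not use database entry order to choose among same-day vital signs.

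The cost is about two sentences. No new data are needed if the case report form carries the time-point labels that the protocol schedule implies. If it does not, affected subjects fall back to an earlier screening reading, which under the screening window could be up to 28 days old. That is a less recent baseline, but an untreated one.
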